5	Claim 1 – No Artificial Sweeteners	Grape fruit drink v. grape juice	Apple fruit drink v. water	No label	Barcode
6	Claim 1 – No Artificial Sweeteners	Grape fruit drink v. grape juice	Apple fruit drink v. water	No label	Graphic
7	Claim 2 – 100% Vitamin C	Grape fruit drink v. grape juice	Apple fruit drink v. water	No label	Text
8	Claim 2 – 100% Vitamin C	Grape fruit drink v. grape juice	Apple fruit drink v. water	No label	Barcode
9	Claim 2 – 100% Vitamin C	Grape fruit drink v. grape juice	Apple fruit drink v. water	No label	Graphic
10	Claim 3 – 100% All Natural	Grape fruit drink v. grape juice	Apple fruit drink v. water	No label	Text
11	Claim 3 – 100% All Natural	Grape fruit drink v. grape juice	Apple fruit drink v. water	No label	Barcode
12	Claim 3 – 100% All Natural	Grape fruit drink v. grape juice	Apple fruit drink v. water	No label	Graphic

In iShoppe, participants will be asked to complete a shopping task for their child aged 1-5 (if more than one child aged 1-5, they will shop for the child who celebrated their birthday most recently). They will have to select between a grape fruit drink and a 100% grape fruit juice (primary outcome, task 1), and they will also have to select between an apple fruit drink and bottled water (secondary outcome, task 1). Both the apple and grape fruit drink will contain the same nutrition claim that the participant was randomized to (if randomized to control, neither fruit drink will have a claim). Participants will also be asked to select between two granola snacks (one experimental, based on randomized arm, and one control with no label) (primary outcome, task 2). After completing the three selection tasks, participants are redirected to a Qualtrics survey measuring reactions to and perceptions of the fruit drinks and granola snack as well as standard demographics.

Study Duration, Enrollment and Number of Subjects

Participation in the study will last approximately 15-20 minutes. The entire study is expected to last a few months.

Study Population

Study population is non-Hispanic white, non-Hispanic Black, and Hispanic any race U.S.-based parents of children between the ages of 1-5 who consume fruit drinks

Inclusion Criteria

1. 18 years old or older
2. Currently reside in the U.S.
3. Have at least one child aged 1-5 years old

4. Child (1-5) with the most recent birthday must have consumed at least one fruit drink in the previous week (7 days)

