5. Self-identify as non-Hispanic white, non-Hispanic Black, or Hispanic any race
6. Panel member on CloudResearch and/or Kantar

STUDY PROCEDURES (what will be done)

Study Steps

Panel Companies will reach out to panel members about this research study. If interested, panel members will complete a screener in Qualtrics to see if they are eligible. If they are not eligible, panel members will be redirected to a termination page indicating they are not eligible to participate. If they are eligible, panel members will be redirected to a consent form. If they agree to the consent form, they will acknowledge their consent by clicking an arrow to proceed to the study.

Qualtrics will randomize the participant to one of the twelve study arms and redirect the participant to iShoppe. In iShoppe the participant will be instructed to shop for their child who is between 1-5 years old. If they have more than one child aged 1-5, they will be instructed to think about the child who had their birthday most recently. They will then be instructed to select two beverages for their child. They will compare the two beverage options for each selection task (grape fruit drink vs. 100% grape fruit juice; apple fruit drink vs. water) and choose one of each. Once they have selected the two beverages, they will be instructed to select a granola snack (control snack with no label vs. experimental snack with label). Once all three products are in the participants' shopping basket, iShoppe will then redirect them to another Qualtrics survey. In the Qualtrics survey, participants will answer questions about their perceptions about and reactions to the fruit drinks and snack, as well as standard demographic questions (see measurements section for more detail). Upon completing the survey, participants will be redirected to a termination link where they will receive an incentive in a type and amount set by the panel company.

Subject Completion/ Withdrawal procedures

A study participant is determined to have completed the study when they have finished and exited the study survey. To withdraw their data from the study, a participant would have to contact the study team or the university IRB.

Screen failure procedures

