Prior to entering into the study, individuals will complete a survey screener. If the individual is younger than 18 years old, does not live in the United States, does not have a child aged 1-5 who consumed at least one fruit drink in the previous week (if multiple children, this pertains to the child with the most recent birthday), or does not self-identify as non-Hispanic white, non-Hispanic black, or Hispanic, they will be deemed ineligible. Such participants will be redirected to a screen notifying them that they are ineligible for the study.

SCREENING AND MONITORING EVALUATIONS AND MEASUREMENTS (how measurements will be made)

Measurements will include results from selection tasks as well as subjective responses by participants. For the primary outcomes for task 1 and task 2, iShoppe will record which beverage (task 1) and which granola snack (task 2) the participant selects, as measured via the virtual store technology. Secondary outcomes for tasks 1 and 2 will include a variety of measurements including participant responses to additional selection tasks, 5-point Likert scale questions, yes/no questions, as well as questions asking participants what % juice the fruit drink is and how much added sugar it contains.

Question	Response Scale
Secondary measures: Task 1	
[Display one fruit drink per their assigned condition (randomly assign to apple or grape).] How healthy would it be for your [age] year old child to drink this beverage every day?	1=Very unhealthy 2=Slightly unhealthy 3=Neither healthy nor unhealthy 4=Slightly healthy 5=Very healthy
How appealing would your [age] year old child find this beverage?	1=Very unappealing 2= Somewhat unappealing 3=Neither appealing nor unappealing 4=Slightly appealing 5=Very appealing
How likely would you be to give this beverage to your [age] year old child?	1=Not at all likely 2=A little likely 3=Fairly likely 4=Very likely 5=Extremely likely
How likely would you be to drink this beverage?	1=Not at all likely 2=A little likely 3=Fairly likely 4=Very likely 5=Extremely likely
[display based on assigned condition, skip for control] This product says, "insert claim text." What does the statement "insert claim text" tell you about this beverage?	[free text]
Do you think this beverage is 100% fruit juice?	0=No 1=Yes
What percentage of this beverage do you think is fruit juice?	[sliding scale of 0 to 100]

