Compared to regular (non-diet) soda , this beverage is...	1=Much less healthy 2=Slightly less healthy 3=Similarly healthy 4=Slightly healthier 5=Much healthier
Compared to 100% fruit juice , this beverage is...	1=Much less healthy 2=Slightly less healthy 3=Equally healthy 4=Slightly healthier 5= Much healthier
Do you think this beverage has added sugar?	0=No [coded as misperception] 1=Yes
[skip if previous Q=0. Will enter 0 as response their response] A can of regular soda contains 8 teaspoons of added sugar. How many teaspoons of added sugar do you think this beverage has?	[free-text entry of #, restrict responses between 0 and 100] _____ teaspoons
This beverage is 20% fruit juice and contains 39 grams (about 9 teaspoons) of added sugar.	1=Not at all misleading 2=A little misleading

How misleading do you think the information on this product is?	3=Somewhat misleading 4=Very misleading 5=Extremely misleading
Secondary measures: Task 2	
[Display labeled snack per their assigned condition] How healthy would it be for your [age] year old child to eat this snack every day?	1=Very unhealthy 2=Slightly unhealthy 3=Neither healthy nor unhealthy 4=Slightly healthy 5=Very healthy
How appealing would your [age] year old child find this snack?	1=Very unappealing 2= Somewhat unappealing 3=Neither appealing nor unappealing 4=Slightly appealing 5=Very appealing
How likely would you be to give this snack to your [age] year old child?	1=Not at all likely 2=A little likely 3=Fairly likely 4=Very likely 5=Extremely likely
How likely would you be to buy this snack in the next week, if it were available?	1=Not at all likely 2=A little likely 3=Fairly likely 4=Very likely 5=Extremely likely
How likely would you be to eat this snack?	1=Not at all likely 2=A little likely 3=Fairly likely 4=Very likely 5=Extremely likely
Which of these snacks do you think would be healthier for your [age] year old child?	1 = (image of product with warning label) 2 = (image of product without warning label) (Randomize their order)
Which of these snacks do you think is higher in added sugar?	1 = (image of product with warning label) 2 = (image of product without warning label) (Randomize their order)
Which of these snacks would you most want to buy for your [age] year old child?	1 = (image of product with warning label) 2 = (image of product without warning label) (Randomize their order)

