### **Analyses**

We will report descriptive results for all outcomes (i.e., means and proportions by group). In all models, the predictor will be a dummy variable indicating whether the participant was randomized to one of the three intervention nutrition claim conditions. For predictions with Likert-style outcomes, we will run linear regression models, one for each outcome. We will examine skewness of the residuals and run ordinal models in sensitivity analyses if residuals

are skewed, retaining the linear models if the pattern of results does not change. For predictions with dichotomous outcomes, we will use the same approach except with logistic regression. We will use the margins command in Stata for significance testing of control vs. each claim separately, as well as each claim compared to the other claims.

We will also report results when controlling for any participant demographic characteristics (including random assignment to two experiments conducted after the primary outcome, but before measurement of some of the secondary outcomes) found to be unbalanced across treatment arms in balance tests, if these results differ substantively from unadjusted results (i.e., changes in statistical significance or direction of effect).

We will examine whether the following participant characteristics moderate the effect claims on the primary outcome:

- a) Age of child shopping for (in years);
- b) Gender of parent (man vs. woman);
- c) Gender of child (boy vs. girl);
- d) Race/ethnicity of parent (White non-Hispanic vs. Black non-Hispanic vs. Hispanic);
- e) Low educational attainment (dichotomized based on sample distribution);
- f) Household income (dichotomized based on sample distribution);
- g) Child's frequency of consuming fruit drinks (above vs. at or below the sample median);
- h) Time spent looking at Nutrition Facts Panel of the beverage;
- i) Seeking vitamin C since COVID-19 pandemic

To test whether these characteristics moderate the effect of claims on selection, we will fit a series of logistic regressions models (one for each potential moderator), with trial arm, the moderator, and their interaction as predictors. We will probe significant interactions by calculating the marginal effect of nutrition claims on the outcome at different levels of the moderating variable.

We will use a critical alpha of 0.05 and statistical tests will be two-tailed. We will correct for multiple comparisons.

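### Task 1 survey outcomes are rated on a randomly shown apple or grape drink, but displayed flavour enters no planned model and no result is given by flavour

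*Protocol*

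**What the plan says.** **The rated drink.** The Protocol's table of secondary measures for Task 1 (Screening and Monitoring Evaluations and Measurements) opens with the instruction "Display one fruit drink per their assigned condition (randomly assign to apple or grape". The items that follow concern that single drink. They include "Do you think this beverage is 100% fruit juice", a 0 to 100 estimate of juice content, and "Compared to 100% fruit juice , this beverage is" on a five-point scale.

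**What came before.** Study Steps gives the two beverage choices as "grape fruit drink vs. 100% grape fruit juice; apple fruit drink vs. water", and every participant makes both. Study Design adds that "Both the apple and grape fruit drink will contain the same nutrition claim that the participant was randomized to", and that the survey comes last: "After completing the three selection tasks, participants are redirected to a Qualtrics survey measuring reactions to and perceptions of the fruit drinks".

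**The analysis.** For Task 1 the SAP (Analyses) states "In all models, the predictor will be a dummy variable" for claim condition, and the Protocol (Statistical Methods) has the same text. Moderators a) to i) apply to the primary outcome only and do not include displayed flavour. Adjustment is limited to demographics and to random assignment in two later experiments. It is made only if these are unbalanced and reported only if results change. The text does not identify the flavour draw as one of those experiments.

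**The concern.** The two flavours reach the survey with different histories. For grape raters, the drink on screen was the product just weighed against 100% juice of the same flavour. For apple raters, it was the product weighed against water. Three items ask directly about juice: whether the drink is 100% juice, what percentage is juice, and how it compares with 100% juice. Answers to these, and the effect of a claim on them, could plausibly differ with that history.

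The Protocol's background says evidence of misperception could inform legal and regulatory action, so these secondary outcomes carry weight. As planned, each result is an average over two contexts and is not described as one. If the claim effect did differ, the planned output would not show it, and a by-flavour split made after the data were seen would look data-driven. A randomised factor that may predict the outcomes is also left out of the models.

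**Working it through.** **1. Outcomes affected.** The Protocol lists 12 Task 1 secondary outcomes. All but the apple-drink-versus-water selection depend on the displayed drink: 12 − 1 = 11.

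**2. The plan's own figure.** About 2,170 participants for f = 0.06, alpha 0.05 and 80% power. Using noncentral F power with λ = N·f² and 1 numerator df, N = 2,182, and power at 2,170 is 0.798. The figure reproduces. It concerns the primary outcome; no sample size is given for the survey outcomes.

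**3. Cell sizes.** Assuming equal allocation, 2,175 / 4 = 543.75 (about 544) per claim arm. With an equal flavour split this is about 272 per claim-by-flavour cell.

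**4. Is the pooled contrast biased?** Flavour is randomised and the shopping sequence is the same in every arm. The expected pooled difference is therefore the mean of the two flavour-specific differences. Assumed example: apple 30% to 40%, grape 20% to 25%. Expected: (10 + 5) / 2 = 7.5 points. A 20,000-run simulation gave 7.50, so there is no bias. Chance imbalance is minor: the SD of the difference in grape share between two arms is √(2 × 0.25 / 543.75) = 0.030, with a 95% limit of 5.9 points. With an assumed 10-point flavour effect, that moves the estimate by about 0.6 point.

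**5. What averaging could hide.** The documents give no misperception rates, so these are assumptions: control 30% in both flavours, apple effect +10 points, one claim versus control, two-sided 0.05 without multiplicity correction.

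| Grape effect | Pooled effect | Power, pooled | Power, interaction |
|---|---|---|---|
| +10 | 10 points | 93% | no interaction |
| +5 | 7.5 points | 75% | 14% |
| 0 | 5 points | 42% | 42% |

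Interaction SE = √(Σ p(1−p) / 271.875) over the four cells. For the middle row: √((0.21 + 0.24 + 0.21 + 0.2275) / 271.875) = 0.0571. Power = Φ(0.05 / 0.0571 − 1.96) = 0.14. With a grape control rate of 20%, interaction power is 15% (grape +5) or 47% (grape 0).

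**6. Smallest difference detectable with 80% power** (control rate 20% to 50%): 7.2 to 8.5 points pooled, 10.4 to 11.9 within one flavour, and 13.6 to 17.0 for the interaction.

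**7. Precision from adding flavour.** Unadjusted SE = √((p₀(1−p₀) + p₁(1−p₁)) / 543.75), using flavour-averaged rates. Stratified SE = half the interaction SE.

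| Apple (control/claim) | Grape (control/claim) | Unadjusted SE | Stratified SE | Ratio | Power |
|---|---|---|---|---|---|
| 30/40 | 30/35 | 0.0286 | 0.0286 | 0.999 | 75% to 75% |
| 30/40 | 20/25 | 0.0274 | 0.0271 | 0.990 | 78% to 79% |
| 40/50 | 15/19 | 0.0280 | 0.0266 | 0.952 | 71% to 75% |
| 40/50 | 10/12 | 0.0272 | 0.0251 | 0.924 | 60% to 67% |

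The last two rows assume gaps between flavours of 25 to 38 points.

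**The case against.** The strongest reply is that nothing is broken. Rating two flavours is a legitimate way to avoid tying results to one product. The claim contrast is valid for the flavour average, only secondary outcomes are involved, and the planned margins testing can be done on the probability scale, so non-collapsibility of the odds ratio is not a serious issue. All of this stands.

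Several stronger readings are tempting, and the documents do not support them:

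- *Grape raters are contaminated and apple raters are clean.* Every apple rater also chose between a grape drink and 100% grape juice before the survey, with the same claim status on both drinks. The halves differ only in whether the rated drink was the one paired with juice.
- *The pooled result understates the claim effect.* No passage fixes a direction. Pairing with juice might make the grape drink seem less juice-like or more so. For the sugar items, the contrast with water could be a cue of its own.
- *A null pooled result could not be interpreted.* It would be a valid null for the flavour average.

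It is also fair that the pairing argument bears mainly on the three juice items. The misleadingness item, for instance, first tells everyone the juice and sugar content. By-flavour estimates are weak too: with apple at 40/50, apple-only power is about 65%, below the pooled 71% in the 40/50 and 15/19 scenario. These points limit the remedy. They do not explain why a randomised factor goes unmentioned.

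**Conclusion.** The point holds as a gap in specification, not as bias. Displayed flavour is randomised, differs in its store pairing in a way relevant to the juice items, and appears in no Task 1 model, moderator list or planned table. The main estimate is a flavour average and should be described as one.

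Whether the claim effect differs by flavour is unknown in size and direction, and every rate used above is an assumption. The precision gain is about 0 to 1% of the standard error if the flavours differ by 0 to about 10 points, and 5 to 8% for gaps of about 25 to 40 points. If flavour has no effect, essentially nothing is lost. The trial has little power to establish an interaction, so the by-flavour results would be descriptive support and not a test. This is an inexpensive improvement to secondary analyses; the primary outcome is untouched.

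**What to change.** Amend the Task 1 analysis text in both the SAP (Analyses) and the Protocol (Statistical Methods):

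1. Include displayed flavour (apple or grape) as a prespecified fixed factor in the models for the 11 survey outcomes, whether or not it is balanced across arms.
2. State that the main claim effect is averaged over flavour. For binary outcomes, report it on the probability scale through the margins step already planned.
3. For the three juice items (100% juice yes/no, percentage juice, comparison with 100% juice), also report the claim effect by flavour with a claim-by-flavour interaction. Label these exploratory because of low power, and keep them outside the multiplicity-corrected family.
4. Describe the flavours as directly paired or not directly paired with juice in the store. Do not present the apple estimate as free of prior exposure to the juice choice.

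The cost is a few sentences and one extra model term, plus an interaction for three items. The flavour draw is made by the survey, so it should already be recorded; confirm that it is exported. Recruitment, participant procedures and the primary analysis do not change.

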In addition, scientific evidence is needed to inform legal actions to reduce deceptive nutrition claims.²⁷ By law, deceptive claims are prohibited. Claims are considered deceptive if they are likely to mislead consumers and when they contain a message that influences a consumer's purchasing decision.^{27,28} For example, "no high fructose corn syrup (HFCS)" claims could lead parents to believe a beverage contains less added sugar, while "made with real fruit juice" claims could lead parents to believe a beverage contains more fruit juice than it actually does. Evidence showing that such claims lead to greater misperceptions and decisions to purchase fruit drinks can inform legal actions, such as a requirement to carry a front-of-pack disclosure on the amount of added sugar or the actual percent of fruit juice contained in the beverage. Similarly, implicit low sugar claims like "lightly sweetened" or "just a tad sweet" are not currently authorized by the FDA. Evidence that these claims lead to misperceptions about a drink's added sugar content and affect parents' purchasing decisions could inform regulations on these claims on high-sugar products, including fruit drinks.

Evidence on nutrition claims has been hindered in part by methodological barriers. Randomized controlled trials (RCTs) are needed to test the causal impact of nutrition claims on decisions to purchase fruit drinks and understand the mechanisms through which behavioral changes occur. However, it can be logistically burdensome and expensive to test the effects of nutrition claims in a real food retail environment. This study will address this methodological gap by examining the causal impact of nutrition claims on parents' decision to purchase fruit drinks in an RCT in an online virtual food store. This controlled but realistic food store environment allows for rigorous experimental control while maintaining high external validity.²⁹⁻³¹

Task 2

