## **Task 1**

### **Predictions**

The aim of Task 1 is to examine how nutrition claims on fruit drink packaging influence US parents' selections, perceptions, and reactions. We have the following predictions:

1. Parents who see a nutrition claim on a fruit drink will be more likely to select the fruit drink (versus 100% fruit juice) than those who do not see a nutrition claim (primary outcome)
2. Parents who see a nutrition claim on a fruit drink will be more likely to select the fruit drink (versus water) than those who do not see a nutrition claim
3. Nutrition claims will lead to greater perceived appeal of fruit drinks
4. Nutrition claims will lead to greater interest in giving fruit drinks to one's child
5. Nutrition claims will lead to greater interest in consuming fruit drinks
6. Parents who see a nutrition claim will be more likely to hold the misperception that the fruit drink is 100% fruit juice
7. Parents who see a nutrition claim will be more likely to hold the misperception that the fruit drink does not have added sugar
8. Nutrition claims will lead to lower estimates of the amount of added sugar people think the product contains
9. Nutrition claims will lead to higher estimates of the percentage of fruit juice people think the product contains
10. Nutrition claims will lead to lower perceived harm of fruit drinks compared to soda
11. Nutrition claims will lead to lower perceived harm of fruit drinks compared to 100% fruit juice
12. Nutrition claims will lead to greater misleadingness of the product packaging

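### Task 1 survey: only the claim conditions get a free-text prompt quoting the claim, and it is listed ahead of the seven items for SAP predictions 6 to 12, so in that order their control-vs-claim contrasts mix package claim and prompt

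*Protocol*

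**What the plan says.** The Task 1 part of the measures table (Protocol, Screening and Monitoring Evaluations and Measurements) shows the parent one fruit drink in the assigned condition. Four rated items come first: healthfulness, appeal to the child, likelihood of giving it, likelihood of drinking it. The fifth item quotes the claim and asks what it tells the parent about the drink. Its routing note reads "display based on assigned condition, skip for control", and no substitute question is given for control.

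Seven scored items follow, starting with "Do you think this beverage is 100% fruit juice" and including "Do you think this beverage has added sugar". The last, on misleadingness, is preceded by a disclosure with no arm restriction: "This beverage is 20% fruit juice and contains 39 grams (about 9 teaspoons) of added sugar".

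The SAP's Task 1 predictions 6 to 12 concern these seven measures. Prediction 7, for example, is "Parents who see a nutrition claim will be more likely to hold the misperception that the fruit drink does not have added sugar". The SAP's Task 1 Analyses section compares control with each claim and the claims with one another. Its only adjustment is for unbalanced participant characteristics, among which it counts assignment to two other experiments.

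**The concern.** The protocol's background says what these outcomes are for: "Evidence showing that such claims lead to greater misperceptions and decisions to purchase fruit drinks can inform legal actions". The quantity wanted is therefore what a claim on a package does to a parent's beliefs. In the listed order, parents in the claim conditions are made to reread and interpret the claim shortly before they are asked about juice and sugar, and control parents are not. A difference from control would then combine the package claim with a survey-induced elaboration of it. A critic of the evidence could say that the questionnaire helped to produce the misperception, and the data could not answer that.

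**Working it through.** The documents give no figure for this point. Their one power figure concerns the primary outcome, which is not affected.

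**Step 1: match items to predictions.** In table order, the seven items after the prompt are:

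| Item after the prompt | SAP prediction |
|---|---|
| 100% juice, yes/no | 6 |
| Percentage juice, 0-100 slider | 9 |
| Compared with soda, 5-point | 10 |
| Compared with 100% juice, 5-point | 11 |
| Added sugar, yes/no | 7 |
| Teaspoons of added sugar | 8 |
| Misleadingness, 5-point | 12 |

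This is the full set 6 to 12, with none missing and none extra. The protocol lists 12 Task 1 secondary outcomes, so 7 of 12 are involved.

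**Step 2: what is not affected.**
- The primary outcome and prediction 2 are store selections, made before "iShoppe will then redirect them to another Qualtrics survey".
- Healthfulness and predictions 3 to 5 are listed before the prompt.
- Claim-vs-claim contrasts have a prompt on both sides.

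**Step 3: can analysis separate the two?** The prompt goes to all three claim conditions (9 of 12 arms) and to no control participant. A model with an intercept, three claim indicators and a prompt indicator has 5 columns but rank 4, because the prompt indicator is the sum of the claim indicators. No covariate adjustment can recover the package effect alone.

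**Step 4: how large would a prompt effect have to be to matter?** This is an illustration for the two yes/no outcomes. The assumptions are mine: equal allocation, no true package effect, control rate p0 of 50% or 30%, and an upward shift d due to the prompt alone.

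- n per condition = 2,175 / 4 = 543.75
- p1 = p0 + d
- SE = sqrt(p0(1 - p0)/n + p1(1 - p1)/n)
- Rejection probability for one claim vs control = P(|Z + d/SE| > z)
- z = 1.960 uncorrected, 2.394 for Bonferroni over the three control contrasts (0.05/3), 2.638 over all six pairwise contrasts (0.05/6)

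The SAP promises a multiplicity correction but names neither method nor family, so both corrections are assumptions.

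Worked case, p0 = 0.50 and d = 0.05: SE = sqrt(0.50 x 0.50/543.75 + 0.55 x 0.45/543.75) = 0.03025; d/SE = 1.653; rejection probability 0.380.

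| p0 | d (points) | SE (points) | Uncorrected | Three contrasts | Six contrasts |
|---|---|---|---|---|---|
| 50% | 3 | 3.030 | 0.168 | 0.081 | 0.050 |
| 50% | 5 | 3.025 | 0.380 | 0.229 | 0.162 |
| 50% | 8 | 3.013 | 0.757 | 0.603 | 0.507 |
| 30% | 3 | 2.816 | 0.187 | 0.092 | 0.058 |
| 30% | 5 | 2.837 | 0.422 | 0.264 | 0.191 |
| 30% | 8 | 2.863 | 0.798 | 0.656 | 0.562 |

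With d = 0 the probability is the nominal level: 0.05, 0.017 and 0.008. The log-odds Wald test that logistic regression uses gives nearly the same uncorrected values: 0.168 / 0.379 / 0.753 at 50% and 0.187 / 0.420 / 0.794 at 30%. I give no figure for the slider, the teaspoon count or the three 5-point items.

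**The case against.** **The order is not stated.** Neither document says that the table order is the survey order. The table is not a full script: it leaves out the demographic questions and does not place the two other experiments. This stands, and it is why the conclusion is conditional. The table does read as a sequence: the teaspoons item depends on the answer before it, the disclosure comes only after the questions it would answer, and randomised order is noted only for the Task 2 image choices. None of this fixes the free-text item's position, but nothing suggests another one.

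**No bias is demonstrated.** This also stands. The prompt repeats words the parent has already met, since "Both the apple and grape fruit drink will contain the same nutrition claim that the participant was randomized to", and the claim is again on the drink displayed for these questions. The added effect could be small. Misleadingness is probably the least exposed, because its wording sends every arm to the information on the product.

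**The probabilities are generic.** They would be the same for any bias of that size, and they depend on the multiplicity correction. With six contrasts, a 3-point shift gives only about 0.05 to 0.06. A wider family of 21 tests (seven outcomes by three control contrasts) gives 0.02 / 0.08-0.10 / 0.35-0.40 for 3 / 5 / 8 points. The figures show sensitivity and are not evidence of bias.

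**Moving the item spoils the free text.** It is the only question asking directly what the claim conveys, and after the move it would follow the juice and sugar items and the disclosure. That loss is real. However, the item is not a listed outcome or a SAP prediction and has no planned analysis, whereas the seven measures behind it are all three.

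**The survey may already have been fielded.** The synopsis speaks of the study partly in the past tense. If so, only the reporting remedy remains.

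**Conclusion.** The concern holds, and it should be fixed. The asymmetric routing and the match to predictions 6 to 12 are plain in the documents. If the listed order is the administered order, the control-vs-claim contrasts on 7 of 12 Task 1 secondary outcomes estimate the claim plus a prompt to elaborate on it, and the two cannot be separated. The size and direction of the prompt's contribution are unknown. Under the stated assumptions, its consequence for the two yes/no outcomes runs from minor at 3 points (0.17 to 0.19 uncorrected, about 0.05 to 0.09 with three to six contrasts) to serious at 8 points (0.76 to 0.80 uncorrected, 0.51 to 0.66 corrected). Confidence is medium because the survey order rests on the table layout alone.

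**What to change.** State the administration order, and place the free-text item after the misleadingness item, so that all seven outcomes are collected under identical questioning in all four fruit-drink conditions. This means reordering one survey item, with no added items, participants or analysis. The price is that the free text no longer captures a spontaneous reading of the claim.

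Two alternatives keep more of the free text but protect less:
- Placing the item just before the disclosure clears six of the seven outcomes and spares the free text the disclosure. It still follows six closed items and leaves misleadingness prompted.
- Giving control a neutral open question balances the act of elaborating, but only claim-condition parents would have a claim quoted to them.

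If data were collected in the listed order, report the control-vs-claim results for predictions 6 to 12 as the effect of the claim plus prompted elaboration, and name this as a limitation. That costs only wording.
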